4.2 OTHER TREATMENTS, EMERGENCY PROCEDURES, RESTRICTIONS

4.2.1 Other treatments and emergency procedures

There are no special emergency procedures to be followed. No additional treatment is planned. However, if adverse events require treatment, the investigator can authorise symptomatic therapy. In those cases, subjects will be treated as necessary and, if required, kept under supervision at the trial site or transferred to a hospital until all results of medical evaluations are acceptable.

4.2.2 Restrictions

4.2.2.1 Restrictions regarding concomitant treatment

In principle, no concomitant therapy is allowed. In particular, concomitant use of drugs known to be metabolized via CYP3A4 or drugs known to prolong the QT interval, are

prohibited. All concomitant or rescue therapies will be recorded (including time of intake on study days) on the appropriate pages of the CRF.

4.2.2.2 Restrictions on diet and life style

While admitted to the trial site, the subjects will be instructed not to consume any foods or drinks other than those provided by the staff. Standardised meals will be served at the times indicated in the [Flow Chart](#). No food is allowed for at least 4 h after intake of BI 425809.

On Day 1 of both treatment periods, starting from 1 h before intake of BI 425809 (i.e. from planned time -1:00) until lunch, fluid intake is restricted to 240 mL of water at planned time -1:00 either with [period 2] or without [period 1] intake of fluconazole), 240 mL with intake of BI 425809, and an additional 240 mL of water at 2 h and 4 h after administration of BI 425809.

In both periods, total fluid intake on Day 1 is restricted to 3000 mL from lunch until 24 h post administration of BI 425809.

Green tea, grapefruits, Seville oranges (sour or bitter oranges) and their juices, and dietary supplements and products containing St. John's wort (*Hypericum perforatum*) are not permitted from 7 days before the first administration of trial medication until after the last PK sampling of the trial.

Alcoholic beverages are not permitted starting 48 h before first trial drug administration until last PK sampling of the trial.

Methylxanthine-containing drinks or foods (such as coffee, tea, cola, energy drinks, or chocolate) are not allowed during in-house confinement at the trial site.

Smoking is not allowed during in-house confinement at the trial site.

Excessive physical activity (such as competitive sport) should be avoided from 7 days before the first administration of trial medication until the end of trial examination.

Direct exposure to the sun or exposure to solarium radiation should be avoided during the entire study.

4.3 TREATMENT COMPLIANCE

Compliance will be assured by administration of all trial medication in the study centre under supervision of the investigating physician or a designee. The measured plasma concentrations of trial medication will provide additional confirmation of compliance.

Subjects who are non-compliant (for instance, who do not appear for scheduled visits or violate trial restrictions) may be removed from the trial and the CRF will be completed accordingly (for further procedures, please see Section [3.3.4.1](#)).

5. ASSESSMENTS

5.1 ASSESSMENT OF EFFICACY

Not applicable.

5.2 ASSESSMENT OF SAFETY

5.2.1 Physical examination

At screening, the medical examination will include demographics, height and body weight, smoking and alcohol history (results not mandatory to be entered into CRF or to be reported), relevant medical history and concomitant therapy, review of inclusion and exclusion criteria, review of vital signs (BP, PR), 12-lead ECG, laboratory tests, and a physical examination. At the end of trial examination, it will include review of vital signs, 12-lead ECG, laboratory tests, and a physical examination.

5.2.2 Vital signs

Systolic and diastolic blood pressures (BP) as well as pulse rate (PR) or heart rate (heart rate is considered to be equal to pulse rate) will be measured by a blood pressure monitor (Dinamap Pro 100, [REDACTED]) at the times indicated in the [Flow Chart](#), after subjects have rested for at least 5 min in a supine position. All recordings should be made using the same type of blood pressure recording instrument on the same arm, if possible.

5.2.3 Safety laboratory parameters

For the assessment of laboratory parameters, blood and urine samples will be collected by the trial site at the times indicated in the Flow Chart after the subjects have fasted for at least 10 h. For retests, at the discretion of the investigator or designee, overnight fasting is not required. Fasting is not required for safety lab C (see Flow Chart and Table [5.2.3: 1](#)).

The parameters that will be determined are listed in Tables 5.2.3: 1 and [5.2.3: 2](#). Reference ranges will be provided in the ISF, Section 10.

Manual differential white blood cell count or urine sediment examinations will only be performed if there is an abnormality in the automatic blood cell count or in the urinalysis, respectively.

Table 5.2.3: 1 Routine laboratory tests

Functional lab group	BI test name [comment/abbreviation]	A ¹	B ¹	C ¹	D ¹
Haematology	Haematocrit	X	X	--	X
	Haemoglobin	X	X	--	X
	Red Blood Cell Count/Erythrocytes	X	X	--	X
	Reticulocytes, absol.	X	--	--	X
	Reticulocytes/Erythrocyte	X	--	--	X
	White Blood Cells/Leucocytes	X	X	--	X
	Platelet Count/Thrombocytes (quant)	X	X	--	X
Automatic WBC differential, relative	Neutrophils/Leukocytes; Eosinophils/Leukocytes; Basophils/Leukocytes; Monocytes/Leukocytes; Lymphocytes/Leukocytes	X	X	--	X
Automatic WBC differential, absolute	Neutrophil, absol.; Eosinophils, absol.; Basophils, absol.; Monocytes, absol.; Lymphocytes, absol.	X	X	--	X
Manual differential WBC (if automatic differential WBC is abnormal)	Neut. Poly (segs); Neut. Poly (segs), absol.; Neutrophils Bands; Neutrophils Bands, absol.; Eosinophils/Leukocytes; Eosinophils, absol.; Basophils/Leukocytes; Basophils, absol.; Monocytes/Leukocytes; Monocytes, absol.; Lymphocytes/Leukocytes; Lymphocytes, absol.				
Coagulation	Activated Partial Thromboplastin Time	X	X	--	X
	Prothrombin time – INR (International Normalization Ratio)	X	X	--	X
Enzymes	AST [Aspartate transaminase] /GOT, SGOT	X	X	X	X
	ALT [Alanine transaminase] /GPT, SGPT	X	X	X	X
	Alkaline Phosphatase	X	X	X	X
	Gamma-Glutamyl Transferase	X	X	X	X
	Creatine Kinase [CK]	X	--	--	--
	Creatine Kinase Isoenzyme MB [only if CK is elevated]	X	--	--	--
Hormones	Thyroid Stimulating Hormone	X	--	--	--
Substrates	Glucose (Plasma)	X	X	--	X
	Creatinine	X	X	--	X
	GFR/ CKD-EPI ³	X	--	--	--
	Bilirubin, Total	X	X	--	X
	Bilirubin, Direct	X	X	--	X
	Protein, Total	X	X	--	X
	C-Reactive Protein (Quant)	X	X	--	X
Electrolytes	Sodium	X	X	--	X
	Potassium	X	X	--	X
Urinalysis ² (Stix)	Urine Nitrite (qual)	X	X	--	X
	Urine Protein (qual)	X	X	--	X
	Urine Glucose (qual)	X	X	--	X
	Urine Ketone (qual)	X	X	--	X
	Urobilinogen (qual)	X	X	--	X
	Urine Bilirubin (qual)	X	X	--	X
	Urine RBC/Erythrocytes (qual)	X	X	--	X
	Urine WBC/Leucocytes (qual)	X	X	--	X
	Urine pH	X	X	--	X
Urine sediment ² (microscopic examination)	Only positive findings will be reported (for instance, the presence of sediment bacteria, casts in sediment, squamous epithelial cells, erythrocytes, leukocytes)				

- 1 A, B, C and D refer to different sets of laboratory parameters. The [Flow Chart](#) details at which time point which set is to be investigated
- 2 Microscopic examination if erythrocytes, leukocytes, nitrite or protein are abnormal in urine
- 3 Estimated glomerular filtration rate according to CKD-EPI formula [\[R12-1392\]](#)

The tests listed in Table 5.2.3: 2 are exclusionary laboratory tests that may be repeated as required. The results will not be entered in the CRF/database and will not be reported in the CTR. Except for drug screening, it is planned to perform these tests during screening only. Drug screening will be performed at screening and prior to each treatment period.

Table 5.2.3: 2 Exclusionary laboratory tests

Functional lab group	Test name
Drug screening (urine)	Amphetamine/MDA
	Barbiturates
	Benzodiazepine
	Cannabis
	Cocaine
	Methadone
	Methamphetamines/MDMA/XTC
	Opiates
	Phencyclidine
	Tricyclic antidepressants
Infectious serology (blood)	Hepatitis B surface antigen (qualitative)
	Hepatitis B core antibody (qualitative)
	Hepatitis C antibodies (qualitative)
	HIV-1 and HIV-2 antibody (qualitative)

To encourage compliance with alcoholic restrictions, a breath alcohol test (e.g. [REDACTED]), [REDACTED] will be performed prior to each [REDACTED] the study at the discretion of an investigator or designee. The results will not be included in the CTR.

The laboratory tests listed in Tables [5.2.3: 1](#) and 5.2.3: 2 will be performed at [REDACTED] [REDACTED] with the exception of drug screening tests. These tests will be performed at the trial site using [REDACTED] Urine Drug Test or a comparable test system.

Laboratory data will be transmitted electronically from the laboratory to the trial site.

5.2.4 Electrocardiogram

Twelve-lead ECGs (I, II, III, aVR, aVL, aVF, V1 - V6) will be recorded using a computerised electrocardiograph ([REDACTED]) at the times provided in the [Flow Chart](#).

To achieve a stable heart rate at rest and to assure high quality recordings, the site personnel will be instructed to assure a relaxed and quiet environment, so that all subjects are at complete rest.

All ECGs will be recorded for a 10 sec duration after subjects have rested for at least 5 min in a supine position. ECG assessment will always precede all other study procedures scheduled for the same time to avoid compromising ECG quality.

All ECGs will be stored electronically on the Muse CV Cardiology System ([REDACTED]) ([REDACTED]). Electrode placement will be performed according to the

method of Wilson, Goldberger and Einthoven modified by Mason and Likar (hips and shoulders instead of ankles and wrists).

All locally printed ECGs will be evaluated by the investigator or a designee. Abnormal findings will be reported as AEs (during the trial) or baseline conditions (at screening) if assessed to be clinically relevant by the investigator. Any ECG abnormalities will be carefully monitored and, if necessary, the subject will be removed from the trial and will receive the appropriate medical treatment.

ECGs may be repeated for quality reasons (for instance, due to alternating current artefacts, muscle movements, or electrode dislocation) and the repeated ECG will be used for analysis. Additional (unscheduled) ECGs may be collected by the investigator for safety reasons.

5.2.5 Assessment of adverse events

5.2.5.1 Definitions of adverse events

5.2.5.1.1 Adverse event

An adverse event (AE) is defined as any untoward medical occurrence in a patient or clinical investigation subject administered a medicinal product and which does not necessarily have to have a causal relationship with this treatment.

An AE can therefore be any unfavourable and unintended sign (including an abnormal laboratory finding), symptom, or disease temporally associated with the use of a medicinal product, whether or not considered related to the medicinal product.

The following should also be recorded as an AE in the CRF and BI SAE form (if applicable):

- Worsening of the underlying disease or of other pre-existing conditions
- Changes in vital signs, ECG, physical examination, and laboratory test results, if they are judged clinically relevant by the investigator

If such abnormalities already pre-exist prior to trial inclusion, they will be considered as baseline conditions and should be collected in the eCRF only.

5.2.5.1.2 Serious adverse event

A serious adverse event (SAE) is defined as any AE which fulfils at least one of the following criteria:

- Results in death
- Is life-threatening, which refers to an event in which the patient was at risk of death at the time of the event; it does not refer to an event that hypothetically might have caused death if more severe
- Requires inpatient hospitalisation
- Requires prolongation of existing hospitalisation
- Results in persistent or significant disability or incapacity
- Is a congenital anomaly/birth defect

- Is deemed serious for any other reason if it is an important medical event when based upon appropriate medical judgment which may jeopardise the patient and may require medical or surgical intervention to prevent one of the other outcomes listed in the above definitions. Examples of such events are intensive treatment in an emergency room or at home for allergic bronchospasm, blood dyscrasias or convulsions that do not result in hospitalisation or development of dependency or abuse

5.2.5.1.3 AEs considered ‘Always Serious’

Cancers of new histology and exacerbations of existing cancer must be classified as a serious event regardless of the time since discontinuation of the trial medication and must be reported as described in [5.2.5.2](#), subsections ‘AE Collection’ and ‘**AE reporting to sponsor and timelines**’.

In accordance with the European Medicines Agency initiative on Important Medical Events, Boehringer Ingelheim has set up a list of further AEs, which, by their nature, can always be considered to be ‘serious’ even though they may not have met the criteria of an SAE as defined above.

The latest list of ‘Always Serious AEs’ can be found in the eDC system, an electronic data capture system which allows the entry of trial data at the trial site. These events should always be reported as SAEs as described above.

5.2.5.1.4 Adverse events of special interest

The term adverse events of special interest (AESI) relates to any specific AE that has been identified at the project level as being of particular concern for prospective safety monitoring and safety assessment within this trial, e.g. the potential for AEs based on knowledge from other compounds in the same class. AESIs need to be reported to the sponsor’s Pharmacovigilance Department within the same timeframe that applies to SAEs, please see Section [5.2.5.2.2](#).

The following are considered as AESIs:

- Hepatic injury
A hepatic injury is defined by the following alterations of hepatic laboratory parameters:
 - o An elevation of AST (aspartate transaminase) and/or ALT (alanine transaminase) ≥ 3 -fold ULN combined with an elevation of total bilirubin ≥ 2 -fold ULN measured in the same blood sample, or
 - o Aminotransferase (ALT, and/or AST) elevations ≥ 10 fold ULN

These lab findings constitute a hepatic injury alert and the subjects showing these lab abnormalities need to be followed up according to the ‘DILI checklist’ provided in the ISF. In case of clinical symptoms of hepatic injury (icterus, unexplained encephalopathy, unexplained coagulopathy, right upper quadrant abdominal pain, etc.) without lab results (ALT, AST, total bilirubin) available, the Investigator should make sure that these parameters are analysed, if necessary in an unscheduled blood

test. Should the results meet the criteria of hepatic injury alert, the procedures described in the DILI checklist should be followed.

5.2.5.1.5 Intensity (severity) of AEs

The intensity (severity) of the AE should be judged based on the following:

Mild: Awareness of sign(s) or symptom(s) that is/are easily tolerated
Moderate: Sufficient discomfort to cause interference with usual activity
Severe: Incapacitating or causing inability to work or to perform usual activities

5.2.5.1.6 Causal relationship of AEs

Medical judgment should be used to determine the relationship, considering all relevant factors, including pattern of reaction, temporal relationship, de-challenge or re-challenge, confounding factors such as concomitant medication, concomitant diseases and relevant history.

Arguments that may suggest that there is a reasonable possibility of a causal relationship could be:

- The event is consistent with the known pharmacology of the drug
- The event is known to be caused by or attributed to the drug class
- A plausible time to onset of the event relative to the time of drug exposure
- Evidence that the event is reproducible when the drug is re-introduced
- No medically sound alternative aetiologies that could explain the event (e.g. pre-existing or concomitant diseases, or co-medications)
- The event is typically drug-related and infrequent in the general population not exposed to drugs (e.g. Stevens-Johnson syndrome)
- An indication of dose-response (i.e. greater effect size if the dose is increased, smaller effect size if dose is reduced)

Arguments that may suggest that there is no reasonable possibility of a causal relationship could be:

- No plausible time to onset of the event relative to the time of drug exposure is evident (e.g. pre-treatment cases, diagnosis of cancer or chronic disease within days / weeks of drug administration; an allergic reaction weeks after discontinuation of the drug concerned)
- Continuation of the event despite the withdrawal of the medication, taking into account the pharmacological properties of the compound (e.g. after 5 half-lives). Of note, this criterion may not be applicable to events whose time course is prolonged despite removing the original trigger
- Additional arguments amongst those stated before, like alternative explanation (e.g. situations where other drugs or underlying diseases appear to provide a more likely explanation for the observed event than the drug concerned)

- Disappearance of the event even though the trial drug treatment continues or remains unchanged

5.2.5.2 Adverse event collection and reporting

5.2.5.2.1 AE collection

Upon enrolment into a trial, the subject's baseline condition is assessed (for instance, by documentation of medical history/concomitant diagnoses), and relevant changes from baseline are noted subsequently.

Subjects will be required to report spontaneously any AEs as well as the time of onset, end time, and intensity of these events. In addition, each subject will be regularly assessed by the medical staff throughout the clinical trial and whenever the investigator deems necessary. As a minimum, subjects will be questioned for AEs (and concomitant therapies) at the time points indicated in the [Flow Chart](#). Assessment will be made using non-specific questions such as 'How do you feel?'. Specific questions will be asked wherever necessary in order to more precisely describe an AE.

A carefully written record of all AEs shall be kept by the investigator in charge of the trial. Records of AEs shall include data on the time of onset, end time, intensity of the event, and any treatment or action required for the event and its outcome.

The following must be collected and documented on the appropriate CRF(s) by the investigator:

- From signing the informed consent onwards until an individual subject's end of trial:
 - All AEs (serious and non-serious) and all AESIs
 - The only exception to this rule are AEs (serious and non-serious) and AESIs in Phase I trials in healthy volunteers, when subjects discontinue from the trial due to screening failures prior to administration of any trial medication. In these cases, the subjects' data must be collected at trial site but will not be entered in the CRF or trial database and will not be reported in the CTR.
- After the individual subject's end of trial:
 - The investigator does not need to actively monitor the subject for AEs but should only report any occurrence of cancer and related SAEs and related AESIs of which the investigator may become aware of by any means of communication, e.g. phone call. Those AEs should, however, not be reported in the CRF.

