Trial product 1 dose mode of admin.	BI 425809, 10 mg film-coated tablets 10 mg in Treatment Test and in Treatment Reference Oral with 240 mL of water after an overnight fast of at least 10 h

Trial product 2	Fluconazole, 200 mg hard capsules
dose	2x 200 mg (= 400 mg fluconazole) once daily during Treatment Test, only
mode of admin.	Oral with 240 mL of water
Duration of treatment	
Treatment Reference: BI 425809, single dose
 
Treatment Test: 2 capsules with 200 mg fluconazole (=400 mg) qd on study day -4 until study day +9 (total of 13 dosing days); on study day 1, BI 425809 (as single dose) will be administered 1 hour after fluconazole
 
The BI 425809 single doses of Treatments Reference and Test will be separated by a wash-out period of at least 16 days.

Statistical methods	
The effect of fluconazole on the pharmacokinetics of BI 425809 will be estimated by the ratios of the geometric means (test/reference) for the primary and secondary endpoints. Additionally, their two-sided 90% confidence intervals (CIs) will be provided. This method corresponds to the two one-sided t-test procedure, each at a 5% significance level. Since the main focus is on estimation and not testing, a formal hypothesis test and associated acceptance range is not specified. The statistical model will be an analysis of variance (ANOVA) on the logarithmic scale including effects for 'subject' and 'treatment'. CIs will be calculated based on the residual error from the ANOVA.
 
Descriptive statistics will be calculated for all endpoints.

FLOW CHART

Period	Visit	Day	Planned time (relative to BI 425809 administration [h:min])	Approximate clock time of actual day [h:min]	Event and comment	Safety laboratory ⁸	PK plasma (BI 425809)	PK plasma (fluconazole)	12-lead ECG	Vital signs (BP, PR)	Questioning for AEs and concomitant therapy ⁵
SCR	1	-21 to -1			Screening (SCR) ¹	A			x	x	
Treatment R (BI 425809 single dose)	2	1	-2:00	07:00	Admission to trial site	B ^{2,9}	x ²	x ²	x ²	x ²	x ²
			-1:00	08:00	240 mL fluid intake						
			0:00	09:00	Administration of BI 425809						
			0:30	09:30			x				
			1:00	10:00			x				
			1:30	10:30			x				
			2:00	11:00	240 mL fluid intake		x				x
			3:00	12:00			x				
			4:00	13:00	240 mL fluid intake, Lunch ³		x				x
			5:00	14:00			x				
			6:00	15:00			x				
			7:00	16:00	Light snack (voluntary)						
			8:00	17:00			x				
			10:00	19:00	Dinner						
			12:00	21:00			x				x

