	2		24:00	09:00	Breakfast (voluntary) ³ , discharge from trial site	B	x				x
	3		47:00	08:00	Ambulatory visit		x				x
	4		71:00	08:00	Ambulatory visit		x				x
	6		119:00	08:00	Ambulatory visit		x				x
	8		167:00	08:00	Ambulatory visit		x				x
	10		215:00	08:00	Ambulatory visit	C	x				x

- Subject must be informed and written informed consent obtained prior to starting any screening procedures. Screening procedures include physical examination, check of vital signs, ECG, safety laboratory (including drug screening), demographics (including determination of body height and weight, smoking status and alcohol history), relevant medical history, concomitant therapy and review of inclusion/exclusion criteria. Pharmacogenetic samples will be collected if needed.
- The time is approximate; the procedure is to be performed and completed within the 3 h prior to BI 425809 drug administration.
- If several actions are indicated at the same time, the intake of meals will be the last action.
- See [Flow Chart \(cont.\)](#) on next page
- AEs and concomitant therapies will be recorded throughout the trial, but will be specifically asked for at the times indicated in the [Flow Chart](#) above.
- Only applicable for Flow Chart for Treatment T
- Only applicable for Flow Chart for Treatment T
- Letters A, B, C and D (in Flow Chart below) define different sets of safety laboratory examinations (for details refer to Section [5.2.3](#)).
- Including urine drug screening and alcohol breath test

FLOW CHART (cont.)

[figure not shown]
Period	Visit	Day	Planned time (relative to BI 425809 administration) [h:min]	Approximate clock time of actual day [h:min]	Event and comment	Safety laboratory ⁸	PK plasma (BI 425809)	PK plasma (fluconazole)	12-lead ECG	Vital signs (BP, PR)	Questioning for AEs and concomitant therapy ⁵
Treatment T (Fluconazole multiple dose + BI 425809 single dose)	3	-4	-97:00	08:00	Fluconazole administration				x		x
		-3	-73:00	08:00	Fluconazole administration						x
		-2	-49:00	08:00	Fluconazole administration						x
		-1	-25:00	08:00	Fluconazole administration	C					x
		1	-2:00	07:00	Admission to trial site	B ^{2,9}	x ²		x ²	x ²	x ²
			-1:00	08:00	Fluconazole administration			x ⁷			
			0:00	09:00	Administration of BI 425809						
			0:30	09:30			x				
			1:00	10:00			x				
			1:30	10:30			x				
			2:00	11:00	240 mL fluid intake		x				
			3:00	12:00			x			x	
			4:00	13:00	240 mL fluid intake, Lunch ³		x				x
			5:00	14:00			x				
			6:00	15:00			x				

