			7:00	16:00	Light snack (voluntary)						
			8:00	17:00			x				x
			10:00	19:00	Dinner						
			12:00	21:00			x				x
		2	23:00	08:00	Fluconazole administration			x ⁷			x
			24:00	09:00	Breakfast (voluntary) ³ , discharge from trial site	B	x		x	x	x
		3	47:00	08:00	Fluconazole administration ⁶		x	x			x
		4	71:00	08:00	Fluconazole administration ⁶	C	x				x
		5	95:00	08:00	Fluconazole administration						x
		6	119:00	08:00	Fluconazole administration ⁶	C	x				x
		7	143:00	08:00	Fluconazole administration						x
		8	167:00	08:00	Fluconazole administration ⁶	C	x		x		x
		9	191:00	08:00	Fluconazole administration						x
		10	215:00	08:00	Ambulatory visit		x				x
FU	4	16 to 30			End of trial (EoTrial) examination ⁴	D			x	x	x

1. See [Flow Chart](#) on previous page.
2. The time is approximate; the procedure is to be performed and completed within the 2 h prior to fluconazole drug administration.
3. If several actions are indicated at the same time, the intake of meals will be the last action.
4. At the end of trial visit the EoTrial examination includes physical examination, vital signs, ECG, safety laboratory, recording of AEs and concomitant therapies.
5. AEs and concomitant therapies will be recorded throughout the trial, but will be specifically asked for at the times indicated in the Flow Chart above.
6. Immediately after PK blood sampling.
7. PK sampling pre-dose (tolerance with respect to planned time: -5 min); fluconazole administration on time.
8. Letters A, B, C and D define different sets of safety laboratory examinations (for details refer to Section [5.2.3](#)).
9. Including urine drug screening and alcohol breath test

TABLE OF CONTENTS

TITLE PAGE	1
CLINICAL TRIAL PROTOCOL SYNOPSIS	2
FLOW CHART	4
TABLE OF CONTENTS	6
ABBREVIATIONS	10
1. INTRODUCTION.....	13
1.1 MEDICAL BACKGROUND	13
1.2 DRUG PROFILE	13
1.2.1 BI 425809	13
1.2.1.1 Non-clinical drug safety.....	13
1.2.1.2 Clinical Safety in Healthy Subjects	14
1.2.1.3 Expected exposure of BI 425809 in this trial.....	15
1.2.2 Fluconazole	16
1.2.3 Residual Effect Period	19
1.3 RATIONALE FOR PERFORMING THE TRIAL	19
1.4 BENEFIT - RISK ASSESSMENT	19
1.4.1 Expected benefit for the target population	19
1.4.2 Procedure-related risks	20
1.4.3 Drug-related risks and safety measures.....	20
1.4.3.1 Risks related to the administration of BI 425809	20
1.4.3.2 Risks related to the administration of fluconazole.....	21
1.4.3.3 Drug-induced liver injury	22

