7.3.4 Safety analyses

Safety will be analysed based on the assessments described in Section 2.2.2.2. All treated subjects (TS, refer to Section [7.2](#)) will be included in the safety analysis. Safety analyses will be descriptive in nature and based on BI standards. No hypothesis testing is planned.

For all analyses, the treatment actually administered (= treatment at onset) to the subject will be used (any deviations from the randomised treatment will be discussed in the minutes of the Report Planning Meeting).

Treatments will be compared in a descriptive way. Tabulations of frequencies/proportions will be used to evaluate categorical (qualitative) data, and tabulations of descriptive statistics will be used to analyse continuous (quantitative) data.

Measurements (such as ECG, vital signs, or laboratory parameters) or AEs will be assigned to treatments (see Section [4.1](#)) based on the actual treatment at the planned time of the measurement or on the recorded time of AE onset (concept of treatment emergent AEs). Therefore, measurements planned or AEs recorded prior to first intake of trial medication will be assigned to the screening period, those between first trial medication intake and end of REP (see Section [1.2.3](#)) will be assigned to the treatment period. Events occurring after the REP but prior to next intake or end of trial termination date will be assigned to 'follow-up'. In case of two or more treatments, the follow-up will be summarized according to the previous treatment. These assignments including the corresponding time intervals will be defined in detail in the TSAP. Note that AEs occurring after the last per protocol contact but entered before final database lock will be reported to Pharmacovigilance only and will not be captured in the trial database.

Additionally, further treatment intervals (analysing treatments) may be defined in the TSAP in order to provide summary statistics for time intervals, such as combined treatments, on-treatment totals, or periods without treatment effects (such as screening and follow-up intervals).

Adverse events will be coded using the Medical Dictionary for Regulatory Activities (MedDRA). Frequency, severity, and causal relationship of AEs will be tabulated by treatment, system organ class, and preferred term. SAEs, AESIs (see Section [5.2.5.1.4](#)), and other significant AEs (according to ICH E3) will be listed separately.

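### Day 1 AE and concomitant-therapy questioning falls at 2, 4 and 12 h in Reference but at 4, 8 and 12 h in Test, with no stated reason: a minor, avoidable difference aliased with treatment

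*Protocol*

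**What the plan says.** Footnote 5 to both Flow Charts sets the rule: "AEs and concomitant therapies will be recorded throughout the trial, but will be specifically asked for at the times indicated" in the chart. Protocol 5.2.5.2.1 makes those times a floor: "As a minimum, subjects will be questioned for AEs (and concomitant therapies) at the time points indicated".

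The two charts differ within the first 12 h after BI 425809. At 2 h the Reference row carries two marks, one for the PK sample and one for questioning ("2:00 11:00 240 mL fluid intake x x"). The Test row at 2 h carries only the PK mark ("2:00 11:00 240 mL fluid intake x"). At 8 h it is the reverse: Reference has the PK mark alone, while Test has PK and questioning. The 4, 12 and 24 h questions appear in both. Test also has questioning at 23 h and on the fluconazole-only days, such as the Day 5 row ("95:00 08:00 Fluconazole administration").

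On the analysis side, protocol 7.3.4 states: "Treatments will be compared in a descriptive way". It plans no hypothesis test and assigns AEs by recorded onset. SAP Table 6.1: 1 defines an on-treatment phase of 11 days for BI 425809 alone and 14 days for BI 425809 with fluconazole. SAP 7.8.1 counts subjects with AEs, not events.

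**The concern.** The sequence is fixed (protocol 3.1 and 4.1.4), so whatever differs between periods differs between treatments. Protocol 3.2 defends the design on the ground that nonspecific time effects are unlikely over a short trial. A difference written into the schedule is not a nonspecific time effect, so that defence does not cover it.

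The first active question after BI 425809 comes at 2 h when the drug is given alone and at 4 h when it is given with the inhibitor. The 8 h question exists only with the inhibitor. Prompted questioning matters most for short, mild complaints, and protocol 1.2.2 names mostly mild headache as the AE most often described in the cited fluconazole trials. Onset time is also used: it assigns the AE to a phase (7.3.4) and informs causality (5.2.5.1.6). With 15 subjects, one additional subject with an event moves a table row by 6.7 percentage points, so readers of the side-by-side counts should know where the periods were not observed alike.

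**Working it through.** **Inputs.** Questioning times are the last column of the two Flow Charts, counted after time 0:00 up to 215 h. Window lengths are from SAP Table 6.1: 1. The planned number is 15 subjects (protocol 3.3).

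**Step 1: the SAP's own figure.** SAP 6.1 says the 14-day window after the second BI 425809 dose ends one hour after the 6-day residual period of the last fluconazole dose. BI 425809 at 09:00 on Day 1 plus 14 days is 09:00 on Day 15. Fluconazole at 08:00 on Day 9 plus 6 days is 08:00 on Day 15. The difference is 1 h, so the figure is reproduced.

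**Step 2: questioning times.**

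| | Reference | Test |
|---|---|---|
| Times (h) | 2, 4, 12, 24, 47, 71, 119, 167, 215 | 4, 8, 12, 23, 24, 47, 71, 95, 119, 143, 167, 191, 215 |
| Prompts to 12 h | 3 | 3 |
| Prompts to 24 h | 4 | 5 |
| Prompts to 215 h | 9 | 13 |
| First prompt | 2 h | 4 h |
| Longest gap, 0 to 12 h | 12 − 4 = 8 h | 4 h |
| Longest gap, 0 to 215 h | 48 h | 24 h |

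The number of prompts by 12 h is equal; one prompt is placed differently. The four extra Test prompts are at 23, 95, 143 and 191 h, the last three being Days 5, 7 and 9.

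**Step 3: after aligning Day 1.** With 8 h added in Reference and 2 h added in Test, both periods have 2, 4, 8 and 12 h, that is 4 prompts each by 12 h. To 24 h the counts become 5 versus 6, because the 23 h Test prompt stays. To 215 h they become 9 + 1 = 10 and 13 + 1 = 14.

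**Step 4: window length.** 11 × 24 = 264 h against 14 × 24 = 336 h, a ratio of 336/264 = 1.27. As an illustration only, assume a constant AE hazard and no drug effect. An 11-day incidence p then becomes 1 − (1 − p)^(14/11) over 14 days:

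- 20% becomes 24.7%
- 30% becomes 36.5%
- 40% becomes 47.8%

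These are assumed incidences, not figures from the documents. They show that the unequal windows alone could separate the two columns by several points.

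**Step 5: scale of one subject.** 1/15 = 6.7 percentage points. This is the step size of the table, not an estimate of bias from the questioning times.

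**The case against.** The strongest reply is that scheduled prompts are only one layer of AE capture. Protocol 5.2.5.2.1 requires subjects to report AEs spontaneously with onset, end and intensity, has staff assess them regularly, and treats the Flow Chart times as a minimum. Subjects are under close surveillance for at least 24 h after BI 425809 in both periods (6.2.2). A general question also covers the preceding interval: a 2 h event in Test can be elicited at 4 h, and an 8 h event in Reference at 12 h. Staff are with the subjects at the unmarked times anyway, drawing blood. The analysis counts subjects with an AE over 11 or 14 days. A shifted prompt therefore changes a count only if a brief event goes unreported spontaneously and at every later question, in a subject with no other AE in that row. Concomitant therapy is in principle not allowed, and any use is recorded with its time of intake on study days (4.2.2.1).

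All of this stands, and it limits the size of the point. A reader might infer that the different times confound the AE comparison, so that no difference between treatments could be attributed to fluconazole. The documents do not support that. Prompt counts to 12 h are equal, three of the questions in the first 24 h are shared, and capture does not depend on prompts alone. Attribution is limited more by the open-label fixed sequence, the 9 versus 13 prompts and the 11- versus 14-day windows, none of which aligning Day 1 would remove.

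What the reply does not supply is a reason for the difference. Equal surveillance in both periods argues for equal times.

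**Conclusion.** The point holds as a minor one. The Day 1 schedules differ without a stated reason, and in a fixed sequence that difference is aliased with treatment. It can slightly affect elicitation and onset timing of brief, mild events. The effect on AE incidence is probably small and cannot be quantified from the documents. The PK endpoints are not at issue: safety is a further objective (protocol 7.1) with descriptive analysis only.

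Two assumptions matter. First, the Flow Charts were read by machine. The Test mark at 3 h falls under vital signs; if a column had shifted, the Test times would be 3, 4, 8 and 12 h, and the periods would still differ. Second, text on expected exposure, rationale and BI 425809 risks is redacted, so the statement that no reason is given applies to the visible text.

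The unequal prompt totals and unequal windows are larger than the Day 1 difference. The extra prompts on Days 5, 7 and 9 follow from the fluconazole dosing visits and cannot be matched without new Reference visits. These asymmetries call for disclosure rather than redesign.

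**What to change.** 1. In both Flow Charts, mark AE and concomitant-therapy questioning at 2:00, 4:00, 8:00, 12:00 and 24:00 after BI 425809. This means adding 8:00 in Reference and 2:00 in Test. Subjects are in-house and PK blood is already drawn at both times in both periods, so no visit or procedure is added.

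2. In protocol 7.3.4 and SAP 7.8.1, add a short note to accompany side-by-side AE frequencies. It should state that questioning at 23 h and on Days 5, 7 and 9 occurs only in Test (9 versus 13 post-dose prompts as scheduled, 10 versus 14 once aligned), and that the on-treatment windows are 11 and 14 days.

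If dosing is already complete, the first change is no longer possible. The note should then also give the Day 1 times actually used. It costs a few sentences in the SAP or the report.
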